#### **E. Potential Scientific Problems:**

One potential limitation is the small sample size. As a pilot study, our main aim is to test feasibility. A more robust, precise demonstration of clinical effectiveness will be pursued in a future project with data used from this study to inform sample size estimates as well as timelines.

Secondly, patients may be re-admitted to hospitals that do not show up in our medical record system (Epic). Insurance claims data would be ideal, but at this stage the added value does not justify the costs required for acquisition. Notably, Epic “Care Everywhere” can detect admissions in the University of Colorado Health system (12 hospitals in Colorado), SCL Health (5), and Centura Health (17). This network of hospitals provides high coverage based on our population, many of whom are homeless and located in a small regional geography.

Another potential limitation is a low follow-up rate at SUDS. This is one major reason for including contingency management as part of our enhanced linkage to care. Regardless, the primary quantitative outcome (hospital re-admission) will not require data from SUDS attendance to measure.

Alternative designs were considered but deemed beyond the scope of this proposal:

- “*Double dummy*” *placebos*, which can minimize bias in both researcher and participant. However, this would be personnel and time-intensive, and due to ketamine’s unique psychoactive effect, patients are unlikely to be successfully blinded.
- *2x2 factorial design*, which could gain information on combinations of multiple interventions, but would unnecessarily weaken inferences and complicate statistical analysis due to interactions in this small sample.
- *30-day in-person evaluation*, which would facilitate additional longitudinal measurement. However, we are not confident that enough patients would show up (or be reachable by telephone) to allow for meaningful analysis.

#### **F. Data Analysis Plan:**

Participants’ demographic and baseline clinical data will be tabulated, and differences between groups will be assessed using a Fisher’s Exact Test for categorical variables and a two-sample t-test for continuous variables. These tests

will help evaluate the effectiveness of randomization. Feasibility outcomes (Aim 1) such as adverse events and acceptability (Likert scale) will be compared for each group using a Fisher's Exact Test and Wilcoxon-Mann-Whitney Test, respectively. Overall recruitment rate and follow-up rate will be tallied at the conclusion of data collection.

For Aim 2, all-cause hospital re-admission within 30-days of discharge will be recorded as a binary outcome. Rates of the two medication intervention groups (XR naltrexone or IV ketamine) will be compared against the group that received enhanced linkage to care alone.

This pilot study may not be sufficiently powered for robust hypothesis testing. By one crude estimate, we could have approximately 80% power to detect a difference between a medication group and the linkage-alone group with about 60 participants assuming a re-admission rate is 25% vs 15%. A larger effect size would increase our power and/or reduce the number of participants required. Regardless, this will provide parameter estimates that can inform a future sample size calculation in a larger effectiveness trial.

For further descriptive purposes, a secondary utilization outcome is risk of 30-day all-cause ED visits. This will be evaluated in a similar manner as hospital re-admissions. Additionally, we are interested in the within-subject difference in readiness-to-change. For those who follow-up, a mean of pre/post differences will be calculated, and a paired t-test will be used to determine if the null hypothesis ( $H_0$ : difference = 0) can be rejected. Drinking behavior will be measured using the Timeline Follow Back method. Binge drinking will be defined as 5+ drinks for men, 4+ for women, and the proportion of binge drinking days since discharge will be calculated for each group. Proportions of positive urine ethyl glucuronide (EtG) will also be tabulated for each group.

Data will be analyzed in SAS.

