### IV. Research Methods

#### A. Outcome Measure(s):

See table 1 for primary and secondary outcomes. In brief, our primary outcomes will be those related to feasibility as well as risk of 30-day all-cause hospital re-admissions. Secondary outcomes include risk of 30-day all-cause emergency department visit,

differences in readiness-to-change, and likelihood of having an alcohol metabolite (EtG) in the urine at follow-up.

*Table 1 Primary and secondary outcomes*

	Study Aim	Description	Instrument(s)
1' feasibility outcomes	1	Recruitment rate (# enrolled / month), follow-up rate, patient acceptability, adverse effects	Chart review, questionnaires
1' clinical outcome	2	Risk of 30-day all-cause hospital re-admissions	Chart review
2' clinical outcomes	2	Risk of 30-day all-cause ED visits	Chart review
	2	Within-subject difference in readiness-to-change 	Questionnaire
	2	Laboratory(+) for alcohol at SUDS	Urine EtG
	2	Percent of binge drinking days  since discharge	Questionnaire

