### C. Study Design and Research Methods

We propose an open-label, pilot feasibility trial (n=45-60), randomizing hospitalized patients to receive XR naltrexone, IV ketamine, or neither prior to hospital discharge, along with enhanced linkage to care. The primary clinical

outcome compared across each of the groups will be 30-day re-admission rates ascertained by chart review (Table 1).

To reduce variability, all participants will undergo a standard addiction consultation that includes behavioral components such as supportive therapy and motivational interviewing. They will also receive enhanced linkage to care (hereon “linkage”) which includes being met by a staff member while in the hospital to begin the clinic intake process and assign a follow-up appointment date. Linkage will also include a contingency management (monetary incentive to follow-up) in their post-hospital transition and receive standard case management and counseling at Substance Use Disorder Services (SUDS) clinic.

ACS team members will identify patients meeting inclusion criteria (Table 2), and – after conducting their usual consultation – approach them about the study. Approximately 900 patients met similar inclusion criteria in 2019 (Query by [name]). After screening for exclusion criteria, informed consent will occur, and initial baseline data will be obtained by “Treatment on Demand” (TOD), a grant-funded team of counselors who are already linking hospitalized patients to addiction care. Consented patients will then be randomized, and the ACS will work with the primary team to order and administer the assigned intervention close to discharge. Meanwhile, a TOD counselor will work to establish a follow-up date within seven days post-discharge. Additional data will be collected immediately after the intervention (for those in one of the two medication groups), at SUDS follow up, and 30-days post-discharge by chart review.

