30-day chart review [data collection point #4]	Research staff	Should check encounters tab as well as “care everywhere” for Denver Metro region.	
 
Admissions (up to 5) within 30 days of discharge date (date, location, up to top 3 main diagnoses based on documentation available).
 
ED visits (up to 5) within 30 days of discharge date (date, location, up to top 3 main diagnoses based on documentation available).
 
AST, ALT obtained at SUDS f/u (if available)
 
Urine EtG obtained at SUDS f/u (if available)
 

Screening: The addiction consult team will attempt to screen patients meeting the inclusion criteria during inpatient admission. We anticipate 10 patients will meet inclusion criteria weekly. They will be assessed for clear exclusion criteria documented in the chart, and if none are noted the patient will be asked if they would like to join the study and complete the screening. If still no exclusion criteria are met and the patient expresses interest, they will be engaged in informed consent. The primary team will be notified by the addiction medicine team. Each combined process of screening and consent is anticipated to require 15 minutes at the end of a typical consultation. The screening window is anticipated to last 5 months.

Randomization: Patients will undergo a simple randomization algorithm to one of three arms.

Intervention:

- **Arm 1:** Receive a single dose of XR naltrexone (380mg) prior to discharge.
- **Arm 2:** Receive a single infusion of IV ketamine (0.5 mg/kg over 40 minutes) prior to discharge.
- **Arm 3:** No single-dose medication
- *All groups will receive enhanced linkage to care that includes contingency management, initiation of biopsychosocial intake, and appointment scheduling. This aspect alone surpasses the current standard of care.*

Contingency Management: Patients will receive a debit card prior to discharge from the hospital. We will utilize a pre-existing system - ClinCard by Greenphire. Participants will receive \$10 upon completion of baseline data, and \$20 upon completion of follow-up data (at SUDS clinic).

Follow up: Patients will be assigned a follow-up within 7 days of discharge at the outpatient addiction clinic (Denver Health SUDS clinic in pavilion K).

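### Adverse effects, a primary outcome, get only a between-group Fisher's test; with 15 to 20 per arm it would usually miss a 20-point excess, and no interval estimate is planned

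*Combined protocol and SAP*

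**What the plan says.** Table 1 (IV.A) gives the primary feasibility outcomes for Aim 1 as "Recruitment rate (# enrolled / month), follow-up rate, patient acceptability, adverse effects". The Data Analysis Plan (IV.F) opens its sentence on them with "Feasibility outcomes (Aim 1) such as adverse events and acceptability (Likert scale" and says they will be compared for each group by Fisher's "Exact Test and Wilcoxon-Mann-Whitney Test, respectively". Adverse events are therefore assigned Fisher's test and acceptability the rank test. The plan does not say whether Fisher's test is pairwise or across all three groups, and it gives no significance level, sidedness, adverse-event definition or expected rate.

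The same section tallies recruitment and follow-up and tabulates proportions with positive urine EtG by group. It states no estimate or interval for adverse events.

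On size, IV.C says "We propose an open-label, pilot feasibility trial (n=45-60), randomizing hospitalized patients", and under Randomization "Patients will undergo a simple randomization algorithm to one of three arms". There are two general cautions: "This pilot study may not be sufficiently powered for robust hypothesis testing" (IV.F) and "One potential limitation is the small sample size" (IV.E). In Table 4 the adverse-event questionnaire (Modified PRISE) is listed only at the visit to the SUDS clinic after discharge.

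**The concern.** For a safety outcome the costly error is to miss a harm. A significance test in small arms makes that error likely, and its p-value does not show how large a harm remains compatible with the data. Aim 1 wants adverse events to yield lessons for a later comparative trial. That needs an event rate per arm and an excess over linkage alone, each with its uncertainty. If the report follows the plan literally, its main statement on the tolerability of two drugs in this setting could be a p-value above 0.05, which readers may take as reassurance.

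**Working it through.** **Plan's own figure.** None exists for adverse events. The only power statement, "we could have approximately 80% power to detect a difference between a medication group and the linkage-alone group with about 60 participants", concerns re-admission at 25% against 15%. It cannot be carried over to adverse events, and it does not reproduce: a two-sided 5% normal approximation with 20 per arm gives about 12%. Nothing below depends on it.

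**Inputs.**
- Total 45 to 60 in three arms (IV.C). Assuming equal allocation, 45/3 = 15 and 60/3 = 20 per arm. Simple randomization lets one arm vary: the 95% range is about 9 to 21 at a total of 45, and 13 to 27 at 60.
- Assumed, not in the documents: two-sided 5%, one drug against linkage alone, and the event rates shown.

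**Events needed for significance.** With no events in the control arm and k in the drug arm, the two-sided Fisher p-value is 2·C(n,k)/C(2n,k).
- n = 20: k = 4 gives 2·4845/91390 = 0.106; k = 5 gives 2·15504/658008 = 0.047.
- n = 15: k = 4 gives 2·1365/27405 = 0.100; k = 5 gives 2·3003/142506 = 0.042.

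At either size, five events against none are needed.

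**Power.** Sum b(x; n, p_drug)·b(y; n, p_control) over all tables (x, y) with Fisher p ≤ 0.05, where b is the binomial probability. The 0% against 20% case reduces to P(X ≥ 5) for X binomial(n, 0.2).

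| Control vs drug | n = 15 | n = 20 |
|---|---|---|
| 0% vs 20% | 16% | 37% |
| 5% vs 25% | 17% | 30% |
| 10% vs 30% | 15% | 24% |
| 10% vs 40% | 33% | 49% |
| 10% vs 60% | 74% | 91% |

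Over the three 20-point rows, the chance of missing the excess runs from 100 − 37 = 63% to 100 − 15 = 85%. From a 10% control rate, 80% power needs a drug-arm rate of about 64% (n = 15) or 53% (n = 20).

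**If the test is across three groups.** With one arm raised (10%, 10%, 30%), power is 23% or 31%. The conclusion is the same.

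**Is the cause the test or the sample size?** Boschloo's less conservative exact test gives 31% or 38% for 5% vs 25%, and 26% or 34% for 10% vs 30%. Most of the shortfall remains, so sample size is the main cause.

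**What intervals would show.** With zero events, the exact two-sided 95% upper limit is 1 − 0.025^(1/n): 21.8% at n = 15 and 16.8% at n = 20. For 6/20 against 2/20 the difference is 20 points, with a Newcombe 95% interval of −5 to 43. For 2/20 against 2/20 the interval is −21 to 21.

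**Denominator.** Only patients who attend SUDS can supply Modified PRISE data. Past attendance was 2 of 17 = 11.8% (Sections II and III), before the enhanced linkage and incentive, so it is not a forecast. If, for illustration, 10 per arm were assessed, power for 10% vs 30% is 6% and the zero-event upper limit is 31%.

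**The case against.** The strongest reply is that this is a pilot that admits its limits. The plan says adverse events will be compared, and it nowhere equates non-significance with safety. It carries the two cautions quoted above. A Fisher comparison needs per-arm counts, from which anyone can compute an interval, and the test is conventional for sparse data.

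Much of this stands. A reader might infer that the plan will declare the drugs tolerable when p exceeds 0.05; the text does not say so. But the power caution leads straight into the re-admission estimate, and the small-sample caution goes on to discuss clinical effectiveness. Neither mentions adverse events or alters their analysis. Being a pilot is also an argument for estimation.

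Three stronger readings fail:
- **That the test's true error rate is about 1%.** This fits a pairwise test with rates near 10% in both arms (0.55% at n = 15, 1.2% at n = 20). The pairwise maximum over all rates is 1.8% or 2.5%, and a three-group test, which the wording allows, reaches 4.4%. A low false-positive rate is in any case not the harm here.
- **That large harms in general are missed.** The last row of the power table shows otherwise. The protocol names ketamine's dissociative effects, and nausea, sleepiness and headache with naltrexone, but gives no rates, so frequent effects could be detected.
- **That Fisher's test is the culprit and should be replaced.** Boschloo's test still gives p = 0.061 for 4/20 against 0/20.

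**Conclusion.** The point holds as a gap in the planned analysis. Adverse effects are a primary outcome, and the only stated analysis could not usually detect an excess of 20 percentage points: it would be missed about 63% to 85% of the time in the three scenarios with control rates of 0% to 10%. A non-significant result would therefore be weak evidence about safety, and the plan provides no interval to show how weak. This rests on equal arms of 15 to 20, a two-sided 5% level, pairwise testing and illustrative event rates. The three-group check moves the figures but not the conclusion, and fewer assessed patients would make matters worse. The documents do not show an intention to treat non-significance as safety. This is a cheap improvement to the analysis and reporting, with no change of design.

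**What to change.** In IV.F, replace the adverse-event part of the Fisher sentence with estimation:
- For each arm, give the number and proportion of patients with any adverse event and with each adverse event, with exact (Clopper-Pearson) 95% intervals.
- Give drug-minus-linkage risk differences for each drug, with 95% intervals by a named method.
- Define the denominator as the patients actually assessed for that event. For Modified PRISE these are the patients who attended the SUDS visit. Report the number assessed beside the number randomized, so that non-attenders are not counted as event-free.
- If a p-value is kept, name the comparison (pairwise or three-group), label it descriptive, and state that non-significance is not evidence of safety. Changing to another exact test is optional and would gain little.

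The cost is a few sentences and a little programming, with no new data. The drawback is that the intervals will be wide and look less reassuring than a p-value: even an arm with no events leaves a true rate of 16.8% to 21.8% possible at 20 or 15 assessed, and about 31% at 10. That is an honest account of what the pilot can show.

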### **II. Background and Significance:**

Alcohol use disorder (AUD) generates approximately 5 million U.S. emergency department visits every year, leading to 2 million hospital admissions and collectively costing the health sector over \$90 billion dollars annually. Because addiction treatment is seldom accessed, hospital admission represents a major opportunity for linkage to care and initiation of oral (PO) naltrexone, a first-line medication shown to improve outcomes such as number of drinking

days, drinks per day, and health care utilization. Denver Health (DH) provides a dedicated addiction consult service (ACS) to assist in these efforts, and the ACS sees hundreds of new consults per month. Yet alcohol-related admissions at DH – estimated at nearly 2,000 per year – show a higher 30-day re-admission rate than the hospital-wide average (Figure 1). This is consistent with a nationally reported re-admission rate for alcohol-related disorders of 21% compared to 14% overall in 2014, ranking it 4th among common diagnoses. Additionally, there is low post-discharge treatment engagement for these patients: one sample of hospitalized DH patients with AUD demonstrated an 11.8% follow-up rate at addiction clinic (chart review).

These sub-optimal transitions of care underscore the limited benefit of oral naltrexone for high-utilizer, safety-net populations who may have social contexts that compromise medication adherence. Different tools are needed that can facilitate post-discharge treatment engagement and reduce re-admissions, goals in line with the DH Center for Addiction Medicine (CAM) and upcoming Hospital Transformation Project application.

The following two pharmaceutical options are well-suited to the hospital setting and complementary to the myriad behavioral strategies to improve treatment compliance and linkage to care:

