### ***Data Collection***

Data will be primarily collected at four time-points (Table 4). Data will be entered by staff into a REDCap database on tablet computers in the hospital and at SUDS clinic. Data collected at enrollment will primarily be descriptive, including demographics, recent drinking history, readiness to change, and various contributing factors to drinking. Immediately after intervention, vital signs,

symptoms, and acceptability will be recorded. Data collected on post-discharge arrival to SUDS clinic will include most 2' clinical outcomes. We will obtain re-admission rate (1' clinical outcome) through chart review, conducted by research team members at 30-days post-discharge.

Table 4 Patient flow and data collection points

Step	Who	Notes	Data collected – staff entered
Patient identified on consult list	ACS	Quick screen that meets inclusion criteria	
↓			
Addiction consult performed	ACS	Evaluation, withdrawal management, medication (though if patient consents to study, will not be prescribed an addiction medication at discharge), brief therapy, referrals, disease screening/harm reduction	
↓			
Screen, consent, randomization	ACS	Formal screen to identify any exclusion criteria. Simple randomization by algorithm	
 
• E-Consent (should include consent to see records in “care everywhere” – some hospitals require permission – when checking for ED visits and re-admissions)
 
• Screening documentation (inclusion and exclusion criteria)
 
• Alcohol-related admissions in last 12 months (date, location, top 3 diagnoses)
 
• Assigned group
 

↓			
Baseline data, referral to SUDS [data collection point #1]	ToD	ToD collects baseline data first, then performs “biopsychosocial intake” and sets up SUDS appointment within 1 week of discharge.  Discharge date is not always predictable;	
 
• Demographics
 
• Baseline clinical data
 
• Depression symptoms baseline (PHQ9 2 wks)
 
• Drinking History 7-days prior to admission (TLFB)
 
• Readiness to change (SOCRATES-8A)
 
• ACE Questionnaire
 

		ACS to review active hospitalized research participants and contact ToD/update date in RedCap as needed.	
↓			

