Intervention administered [data collection point #2]	RN, ACS	
For 'linkage-alone' group, data to be entered following consult.
 
For NTX group, intervention administered prior to discharge (could be same day as consent). Vitals immediately preceding and 40 min post- injection. Data collected after administration.
 
For KET group, intervention administered prior to discharge (could be same day as consent), though should have no food for at least 3 hours (~50% gastric emptying). Vitals immediately preceding, after completion, and 2 hours following end of intervention.
	
 
Vital signs (HR, BP, O2): linkage-alone group- baseline only, recorded after consult. NTX group- baseline, 40 min after administration. KET group- baseline, end of administration (~40min), 2 hours after end of administration.
 
Most recent AST, ALT
 
UDS-5 data
 
[for KET] Dissociative symptoms (CADSS) after administration (40 min)
 
[for NTX and KET] Acceptability of intervention (10-point Likert) after administration
 
[for NTX and KET] Readiness to change (SOCRATES-8A) after administration (40 min)
 
 
ORDER: CMP (if not already obtained), UDS-5 (if not already obtained)
 
ORDER in discharge orders (outpatient): CMP, UDS-5, urine EtG (if not already ordered)

↓			
Presentation to SUDS, data entered, contingency management reward administered [data collection point #3]	SUDS staff	
Upon presentation, staff to collect study data. After completion, will receive contingency management reward.
 
Then patient to complete standard intake/follow-up visit, if willing.
	
 
Drinking History since discharge (TLFB since discharge)
 
Depression symptoms (PHQ9 modified to read "since discharge.")
 
Readiness to change (SOCRATES-8A)
 
[for KET] Dissociative symptoms (CADSS)
 
Adverse Events (Modified PRISE)
 
Acceptability of intervention (10-point Likert)
 

		Staff to instruct patient to present to the clinic laboratory (e.g. pav G) for CMP after the visit.	
 
Contingency management feedback (10-point Likert, open ended)
 

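### The plan does not say how a death without re-admission is handled, and the 30-day chart review has no field that would record one

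*Combined protocol and SAP*

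**What the plan says.** Section IV.F (Data Analysis Plan) defines the primary clinical outcome: "all-cause hospital re-admission within 30-days of discharge will be recorded as a binary outcome". Section IV.C (Data Collection) says it is obtained "through chart review, conducted by research team members at 30-days post-discharge".

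Table 4 lists what that review collects:
- "Admissions (up to 5) within 30 days of discharge date", with date, location and diagnoses;
- "ED visits (up to 5) within 30 days of discharge date", with the same details;
- AST and ALT from the clinic visit, if available;
- "Urine EtG obtained at SUDS f/u (if available").

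Adverse effects are one of the primary feasibility outcomes in Table 1. The instruments given for that row are chart review and questionnaires. In Table 4, the only adverse-event form after discharge, "Adverse Events (Modified PRISE"), is listed at presentation to the SUDS clinic. On timing, the plan says "Patients will be assigned a follow-up within 7 days of discharge at the outpatient addiction clinic".

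The protocol text nowhere mentions death, mortality or vital status.

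**The concern.** A yes/no variable built from admissions found in the chart has no third value. A patient who dies at home on day 12 has no admission to find and so is recorded like a patient who did well. Because the hypothesis is a lower re-admission rate in the medication arms, such a death would sit on the favourable side of the comparison.

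The safety side matters at least as much. Section IV.F plans to compare adverse events between groups with Fisher's exact test. If the listed forms are the only source, that comparison would lack the most serious events in patients who do not reach the clinic, and in everyone after the visit. XR naltrexone is described in section II as a 30-day product, whereas the adverse-event form is planned for the first week.

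The pilot's estimates are also meant to inform the sample size of a larger trial, so an endpoint that is silent on death would carry over into that design.

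**Working it through.** **1. Can any planned record capture a death after discharge?**

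| Where the death occurs | 30-day chart review (Table 4) | Clinic adverse-event form |
|---|---|---|
| During a re-admission | Counted as a re-admission; no field for the death | Not captured |
| In an ED, not admitted | Entered as an ED visit; no field for the death | Not captured |
| Outside any hospital contact | No entry | Not captured |

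The clinic form cannot fill the gap, for two reasons. A patient who has died, or is seriously ill, does not attend. For those who do attend, days 8 to 30 fall after a visit held on schedule. Attendance may also be low: a local sample "demonstrated an 11.8% follow-up rate at addiction clinic". Section III gives the counts, 2 of 17, and 2/17 = 11.8% reproduces the figure. It predates enhanced linkage, so attendance in the trial may be higher.

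Section IV.E records that a day-30 in-person evaluation was considered and rejected. It also says that the re-admission outcome does not need clinic attendance. The chart review is therefore the only planned look at every participant at day 30.

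**2. Size of one death without re-admission**

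Inputs: total n = 45 to 60 in three arms (section IV.C), so about 15 to 20 per arm if the arms come out equal; assumed rates 25% and 15% (section IV.F), a difference of 10 points.

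Shift in an arm's proportion = 1/n:
- 1/20 = 5.0 points, half of the assumed difference;
- 1/15 = 6.7 points, two thirds of it.

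Illustration with 20 per arm, linkage-alone 5/20 = 25% and a medication arm 3/20 = 15%, with deaths without re-admission in the medication arm only:

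| Deaths | Left as not re-admitted | Re-admission or death | Excluded |
|---|---|---|---|
| 1 | 3/20 = 15.0%, difference 10.0 | 4/20 = 20.0%, difference 5.0 | 3/19 = 15.8%, difference 9.2 |
| 2 | 3/20 = 15.0%, difference 10.0 | 5/20 = 25.0%, difference 0 | 3/18 = 16.7%, difference 8.3 |

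**3. How likely is a death?**

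The documents give no 30-day mortality. Assume q = 0.5% to 2%, for deaths of any kind. Expected deaths = N × q; chance of at least one = 1 − (1 − q)^N.

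| N | Expected deaths | Chance of at least one |
|---|---|---|
| 45 | 45 × 0.005 = 0.2 to 45 × 0.02 = 0.9 | 1 − 0.995^45 = 20% to 1 − 0.98^45 = 60% |
| 60 | 60 × 0.005 = 0.3 to 60 × 0.02 = 1.2 | 1 − 0.995^60 = 26% to 1 − 0.98^60 = 70% |

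Only deaths without re-admission touch the primary proportion. If half of the deaths were of that kind (a further assumption), q falls to 0.25% to 1%, and with N = 60 the chance is 1 − 0.9975^60 = 14% to 1 − 0.99^60 = 45%.

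**The case against.** Three stronger readings are tempting, and the documents do not support them.

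- **That the plan has a rule scoring death as a success.** It has no such rule and does not use that word. It is silent, and not re-admitted is simply what the variable yields if nobody decides otherwise.
- **That such a patient is misclassified.** The endpoint is all-cause re-admission, and someone who died without re-admission was not re-admitted. The 5.0 to 6.7 points are the distance between two endpoints, not an error in the planned one. Which endpoint to report is a choice of estimand.
- **That adverse events after discharge come only from the clinic questionnaire.** Table 1 names chart review among the instruments for the row that includes adverse effects, and section IV.C says that data are primarily, not solely, collected at the four time-points. A member of the research team might well note a death. But Table 4 gives the review no field for it, so the two tables do not match.

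There is also a case that the issue is small. Few deaths are expected. Eligibility removes some higher-risk patients, such as those over 65 or with decompensated liver failure. The exact 95% interval for 3/20 runs from about 3% to 38%, so a 5-point shift is small beside the imprecision that the plan acknowledges. The main aim is feasibility. All of this stands, and it limits how much the primary estimate can be said to suffer. It does not answer the safety point: adverse effects are themselves a primary feasibility outcome, and no listed field requires any post-discharge death to be recorded as one.

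Finally, a chart field helps only if the record learns of the death. That stands too, and it shapes the fix.

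**Conclusion.** The concern holds as a gap in outcome definition and safety capture. Handling of death without re-admission is unspecified, and the default gives such a patient the same value as one who stayed well. Followed as written, Table 4 requires no record of deaths or serious events in patients who miss the clinic visit, or after it; an ED death would appear only as an ED visit.

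Each death without re-admission puts 5.0 points (20 per arm) to 6.7 points (15 per arm) between the two ways of counting, assuming equal arms. How often this would arise rests on an assumed mortality, since the documents supply none, and the 20% to 70% span above covers deaths of every kind. A reader might infer that the planned comparison is biased. The documents do not show that: they give no information on how many deaths to expect or in which arm. The change should be made because it costs little and because a rule chosen after a death in an open-label trial would be post hoc.

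**What to change.** 1. Add vital status to the 30-day chart review for all randomized patients: alive, dead or unknown, with date and source. State that the absence of a record is not read as alive.
2. Add serious adverse events to the same review, so that Table 4 matches the instruments in Table 1.
3. Report deaths and serious adverse events by arm, with the number whose vital status is unknown.
4. Keep the primary proportion as it is, and pre-state re-admission or death within 30 days as a companion result.

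The cost is a few extra fields in a review already planned for every participant and one extra row in the results table, with no new visit or contact. The limit is that deaths outside the linked record systems described in section IV.E may still be missed, which is why the unknown category and the source field are needed.
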